**Statistical Considerations:**

This is an open label, phase II clinical trial to evaluate the safety and efficacy of TAK228 in patients with relapsed lymphoma. The maximum numbers of patients that will be recruited are 75 for the phase II.

The primary objective of trial is to determine the best overall response rate, defined as the combination of complete (CR) and partial (PR) response rates in patients with relapsed lymphoma when treated with TAK228. The secondary objectives are to define the safety & tolerability, overall survival, progression free survival, duration of response, determination of response associated clinical characteristics, of TAK228 in patients with relapsed lymphoma.

The overall response assessment at 2 cycles will be utilized to determine if additional accrual in each phase II cohort is warranted, but will not be the primary endpoint.

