**Cohort A**

Cohort A will be defined as aggressive lymphoma (diffuse large b cell lymphoma, follicular grade 3b, transformed lymphomas, and mantle cell lymphoma). Clinical experience with mTORC1 inhibitors in relapsed aggressive lymphoma is variable, but is most commonly reported to be 28-38% ORR.(17) It is assumed that TAK228 will have a target overall response rate at 2 cycles of 35% for this patient cohort. A response rate of 10% or lower is considered a failure and the new regimen will be rejected under this circumstance.

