### **Cohort I**

Cohort I will be defined as indolent lymphoma (follicular lymphoma grade 1 – 3a, small lymphocytic lymphoma, and marginal zone lymphoma). Clinical experience with mTORC1 inhibitors in relapsed indolent lymphoma is variable, but is most commonly reported to be 11-54% ORR.(17) It is assumed that the new regimen will have a target overall response rate at 2 cycles of 45%. A response rate of 20% or lower is considered a failure and the new regimen will be rejected under this circumstance.

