### **Phase II design:**

During the phase II study, patients will be treated with TAK228 at the MTD established in the sponsored trials. Three independent cohorts of patients will be enrolled: 1) patients with aggressive lymphoma (diffuse large B cell lymphoma, follicular grade 3b, transformed lymphomas, and mantle cell lymphoma); 2) patients with indolent lymphoma (follicular lymphoma grade 1 – 3a, small lymphocytic lymphoma, and marginal zone lymphoma); and 3) patients with Hodgkin lymphoma. We will run the three cohorts as three parallel trials. The maximum number of patients needed for each cohort is 25.

For each of the patient cohort, the overall response (OR) at two cycles and dose modifications required based upon toxicity (referred to below as reason for dose modification) at one cycle will be monitored. Simultaneously using Bayesian stopping boundaries calculated based on Beta-Binomial distributions. Independence was assumed between OR and Reason for dose modification.

For each of the patient cohort, the overall response (OR) at two cycles and dose modifications required based upon toxicity (referred to below as reason for dose modification) at one cycle will be monitored. Simultaneously using Bayesian stopping boundaries calculated based on Beta-Binomial distributions. Independence was assumed between OR and reason for dose modification.

For cohorts A) and H), TAK228 will be considered promising if it yields an OR rate of 35% at two cycles and a reason for dose modification rate of 30% at one cycle. A sample size of 25 in each patient cohort ensures that, if the cohort is not terminated early, a posterior 90% credibility interval for overall response rate will have width of 0.297 at most, under the assumption of a 35% of OR rate. The prior probabilities of OR and reason for dose modification for the experimental regimen are modeled by beta distributions (*Beta*(0.7,1.3) and *Beta*(0.6,1.4), respectively). Denoting probabilities of OR rate and reason for dose modification rate by (pOR , pReason for dose modification) Confidential, the following decision criteria will be applied: Stop the trial if  $\text{Prob}(pOR < 35\% | \text{data}) > 0.95$  or  $\text{Prob}(p\text{Reason for dose modification} > 30\% | \text{data}) > 0.95$ .

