Patients will be monitored by a cohort size of 5 after the first 15 patients according to the following stopping boundaries for OR at two cycles and reason for dose modification at one cycle. If the number of responses required for moving the trial to next stage has not been achieved, the patient enrollment will be halted until enough responses observed.

For cohorts I), TAK228 will be considered promising if it yields an OR rate of 45% at two cycles and a REASON FOR DOSE MODIFICATION rate of 25% at one cycle. A sample size of 25 ensures that, if the cohort is not terminated early, a posterior 90% credibility interval for overall response rate will have width of 0.310 at most, under the assumption of a 45% of OR rate. The prior probabilities of OR and REASON FOR DOSE MODIFICATION for the experimental regimen are modeled by beta distributions ( $Beta(0.9,1.1)$  and  $Beta(0.5,1.5)$ , respectively). Denoting probabilities of OR rate and REASON FOR DOSE MODIFICATION rate by ( $p_{OR}$ ,  $p_{Reason\ for\ dose\ modification}$ ), the following decision criteria will be applied: Stop the trial if  $Prob(p_{OR} < 45\% \mid data) > 0.95$  or  $Prob(p_{Reason\ for\ dose\ modification} > 25\% \mid data) > 0.95$ .

Patients will be monitored by a cohort size of 5 after the first 15 patients according to the following stopping boundaries for OR at two cycles and REASON FOR DOSE MODIFICATION at one cycle. If the number of responses required for moving the trial to next stage has not been achieved, the patient enrollment will be halted until enough responses observed.

Patients who are treated on study and have at least 1 disease restaging study prior to termination of study participation will not be replaced with an additional patient added to their disease cohort. Patients who are treated on study and fail to have at least 1 disease restaging study prior to termination of study participation will be replaced with an additional patient added to their disease cohort at the discretion of the principle investigator.

The duration of the study as a whole is defined first patient to start the screening period to the last patient to conclude their therapeutic period. The anticipated accrual is 3 patients per month on this trial. Thus, accrual for the study is expected to be complete in approximately two years. The total duration of the study is anticipated to be approximately three years.

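### Does the plan need a success criterion for best overall response, when its targets and its definition of promising are set on response at two cycles?

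*Combined protocol and SAP*

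**What the plan says.** Statistical Considerations gives the primary objective as to "determine the best overall response rate, defined as the combination of complete (CR) and partial (PR) response rates". It then says that response at two cycles is used to judge "if additional accrual in each phase II cohort is warranted, but will not be the primary endpoint".

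The numerical targets name two cycles. Cohort A has a "target overall response rate at 2 cycles of 35% for this patient cohort", Cohort H has the same value, and Cohort I has a "target overall response rate at 2 cycles of 45" per cent. The Phase II design section repeats them: "TAK228 will be considered promising if it yields an OR rate of 35% at two cycles" for A and H, and "TAK228 will be considered promising if it yields an OR rate of 45% at two cycles" for I. Each of these two sentences goes on to add a dose-modification rate at one cycle (30% for A and H, 25% for I), so the definition is joint.

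Other figures carry no time point:
- the historical rates, such as "most commonly reported to be 28-38% ORR" in Cohort A;
- the failure rates, such as "A response rate of 10% or lower is considered a failure and the new regimen will be rejected under this circumstance" in Cohorts A and H, with 20% in Cohort I;
- the 90% credible-interval widths that justify 25 patients per cohort.

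The Efficacy Analysis section is descriptive, with regression and time-to-event methods and no response threshold. The Protocol Monitoring Plan links the efficacy targets to early closure of cohorts.

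**The concern.** Read quickly, the plan names one primary endpoint and sets its bar on another. If the two-cycle targets serve accrual only, no stated target is left for best response. If they are also the verdict on the drug, that verdict rests on an endpoint the plan says is not primary.

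Restaging continues before cycles 5, 7, 9 and 11 (Evaluation During Study), so a patient can first respond after cycle 2. Best response can therefore exceed two-cycle response but never fall below it. The same 25 patients could miss 35% on one measure and reach it on the other. The Rationale says the trial should pick out subtypes with high response rates for later studies, so an ambiguous label could affect which subtype is taken forward. The plan also does not say whether to yield a rate means an observed proportion or a posterior probability.

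**Working it through.** **1. The plan's own precision figures.** Inputs from Phase II design: n = 25; response priors Beta(0.7, 1.3) for A and H and Beta(0.9, 1.1) for I; assumed rates 35% and 45%. The posterior is Beta(a + x, b + n − x) with x = n × rate.
- A, H: x = 8.75, Beta(9.45, 17.55), equal-tailed 90% width 0.2966 (stated 0.297).
- I: x = 11.25, Beta(12.15, 14.85), width 0.3099 (stated 0.310).

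Both reproduce. Over all possible counts out of 25 the width never exceeds 0.311 in any cohort, so the sample-size justification holds almost unchanged for best response.

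**2. The two-cycle stopping rule.** The rule stops a cohort when Prob(rate < target | data) > 0.95, with looks after 15 patients and then every 5. The boundary tables are not in the available text, so I derived the boundaries.
- A, H: stop at ≤2/15 (posterior probability 0.970) or ≤3/20 (0.977).
- I: stop at ≤3/15 (0.975) or ≤5/20 (0.965).

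Chance of crossing for response by 20 patients, by exact binomial recursion:

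| True two-cycle rate | A, H | I |
|---|---|---|
| At the failure rate (10%; 20%) | 89.2% | 82.0% |
| At the target (35%; 45%) | 7.5% | 6.9% |

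The targets therefore do the accrual job given to them.

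**3. How often the two endpoints could give different labels.** This needs two assumptions that are not in the documents: the share of responses visible at two cycles (90/80/70%), and a reading of the target as an observed rate, so at least 9/25 (25 × 0.35 = 8.75) or 12/25 (25 × 0.45 = 11.25). I used an exact trinomial model (response by two cycles, later response, none) in blocks of 15, 5 and 5. Each futility crossing was treated as final and toxicity stopping was ignored. With the two-cycle rate at target, best response is the target divided by the share: 38.9/43.8/50.0% (A, H) and 50.0/56.3/64.3% (I).

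| Share visible at two cycles | 100% | 90% | 80% | 70% |
|---|---|---|---|---|
| A, H: complete 25, below 9 at two cycles, at least 9 on best response | 0 | 14.7% | 27.8% | 36.2% |
| I: same with 12 | 0 | 19.3% | 36.7% | 45.6% |

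**4. The joint definition.** Take the dose-modification rates at 30% and 25%, independence as the plan assumes, and the observed rate at or below those values (≤7/25, ≤6/25). With toxicity looks at 15 and 20 (stop at ≥8/15 or ≥10/20 in A and H; ≥7/15 or ≥9/20 in I), that half is met with probability 0.51 (A, H) and 0.56 (I). Multiplying the table above by 0.51 or 0.56 gives joint-label disagreement of about 8/14/19% (A, H) and 11/21/26% (I).

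**5. What moving the label would do.** With the two-cycle rate at target, the chance of completing 25 patients and reaching the count is:

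| | Two-cycle response | Best response (90/80/70% visible) |
|---|---|---|
| A, H | 53% | 68/81/89% |
| I | 46% | 65/82/91% |

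**6. If 35% and 45% described best response instead.** The two-cycle rate would then be the target times the visible share, and futility crossing by 20 patients would be 12.6/20.2/30.6% (A, H) and 13.8/24.5/39.1% (I).

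**The case for a change.** The strongest case for a change is that the plan is not written as pure estimation. It states targets, failure rates and rejection of the regimen, and it calls the drug promising rather than the cohort open. Naming the endpoint for each figure would cost a sentence or two and no new scans. The accrual effect is also not always small: under the reading in step 6, a cohort whose best response rate is exactly on target could be stopped nearly two times in five.

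The textual point stands: nothing explicitly links a target to best response. The failure rates might, since they name no time point, but they directly follow two-cycle targets and the plan does not say. A clarifying sentence would be helpful.

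The rest does not carry a change. The step 6 reading goes against the text, which attaches two cycles to every target. No action is attached to the word promising, and its sentences sit in the paragraphs that set up the stopping boundaries, with response priors whose means are those same targets (0.7/2 = 0.35; 0.9/2 = 0.45). A stopped cohort still contributes its best response rate, because Population for Analysis includes everyone who received a dose.

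**Conclusion.** No change to the plan is needed. Followed as written, it estimates best overall response in each cohort with a 90% interval about 0.30 to 0.31 wide under its own assumptions, and it uses an earlier response to decide whether to keep enrolling. That division of roles is stated, and an early-response gate is legitimate. A single-arm estimation aim does not require a success threshold. What is missing is detail that analysts can supply sensibly: report best response with its interval as the primary result, and treat the two-cycle targets as monitoring parameters.

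The one substantive alternative, judging promise on best response, is a trade-off. At unchanged targets it eases the hurdle by about 15 to 36 percentage points in A and H (68 − 53; 89 − 53) and 19 to 45 in I (65 − 46; 91 − 46), and it delays the verdict.

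The label disagreement of 15–36% and 19–46% for response alone, or about 8–19% and 11–26% for the joint definition, depends on the assumed 90–70% visible share and on count cut-offs the plan does not state; it is zero if all responses are visible at two cycles. The accrual effect is small (7.5% and 6.9% at target) provided 35% and 45% describe the two-cycle rate, as the text says they do.

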##### Rationale: (Be as concise as possible)

The mTOR pathway is an active target in multiple lymphoma subtypes. mTOR activity has been shown to be increased in nearly all lymphoma subtypes, including diffuse large B cell, mantle cell, and Hodgkin

lymphomas. The rapalog mTOR inhibitors (Temsirolimus and Everolimus) directly effect mTORC1 and have demonstrated promising efficacy in multiple lymphoma subtypes.

Temsirolimus is approved in Europe for mantle cell lymphoma, and has shown promising responses in diffuse large b-cell, follicular, and other indolent lymphomas. Everolimus has also shown promising responses in relapsed aggressive lymphoma. In addition, Everolimus has shown impressive response in relapsed/refractory Hodgkin lymphoma.

It is now known that inhibition of mTORC1, although effective for a portion of patients with lymphoma, leads to transient benefit at best, and perhaps even tumor growth for some cancers. Demonstrating the complexity of the crosstalk found in this pathway, mTORC1 inhibition can lead to activation of the PI3K pathway due to mTORC2 negative feedback, resulting in phosphorylation of Akt.

We believe inhibition of both mTORC1 and mTORC2 with TAK228 may result in a significant improvement in the efficacy seen to date with mTORC1 inhibitors in lymphomas. This clinical trial is based on: 1) the known promising activity of mTORC1 inhibitors in various subtypes of lymphomas, 2) the known escape/resistance mechanism that cancer utilizes to overcome mTORC1 inhibitor via mTORC2 stimulation of Akt, and 3) the early signal of excellent tolerance and efficacy of TAK228 in clinical trials thus far.

It is our hypothesis that TAK228 will result in response rates higher than previously seen with rapalogs, with acceptable tolerability. The goal of our trial is to identify lymphoma subtypes with high response rates for future clinical trials, either combined with current standard therapies or with novel targeted agents.

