### Analysis Plan

For each patient cohort, summary statistics will be provided for continuous variables such as age. Frequency tables will be used to summarize categorical variables such as gender, histology, response, toxicity type and severity. Logistic regression will be utilized to assess the effect of patient prognostic factors on the response rate and the toxicity rate. The distribution of time-to-event endpoints, such as time to progression and overall survival, will be estimated using the method of Kaplan and Meier. Comparison of time-to-event endpoints by important patient characteristics will be made using the log-rank test.

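### Do the 10%/20% rejection limits and the 35%/45% targets leave a cohort of 25 without an efficacy verdict?

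*Combined protocol and SAP*

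**What the plan says.** The Cohort A section states: "A response rate of 10% or lower is considered a failure and the new regimen will be rejected under this circumstance". The Cohort H section says the same. The Cohort I section states: "A response rate of 20% or lower is considered a failure and the new regimen will be rejected under this circumstance". None of these gives a count, a probability or a time of assessment.

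Under Phase II design, TAK228 in A and H is "promising if it yields an OR rate of 35% at two cycles and a reason for dose modification rate of 30% at one cycle", and in I it is "promising if it yields an OR rate of 45% at two cycles and a REASON FOR DOSE MODIFICATION rate of 25% at one cycle". The decision criteria that follow are stopping criteria. For efficacy, a cohort stops if the posterior probability that the response rate lies below 35% (A/H) or 45% (I) exceeds 0.95. Looks come every 5 patients after the first 15, up to 25 per cohort. If too few responses have been seen, "the patient enrollment will be halted until enough responses observed".

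Statistical Considerations makes best overall response the primary objective and says the two-cycle assessment "will be utilized to determine if additional accrual in each phase II cohort is warranted, but will not be the primary endpoint". The Analysis Plan describes reporting: "Frequency tables will be used to summarize categorical variables such as gender, histology, response, toxicity type and severity". Neither it nor Efficacy Analysis gives an end-of-cohort efficacy verdict. The Rationale says what the results are for: "The goal of our trial is to identify lymphoma subtypes with high response rates for future clinical trials".

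**The concern.** The plan uses decision language (rejected, promising) with two sets of limits, and the 10%/20% limits do not enter the formal rule. Suppose the 0.95 rule is applied at 25 patients and promising means an observed rate at or above target. Results between the two cuts then have no label, although the posterior probability that response exceeds the failure rate is 0.983 to 0.999 there in A/H and 0.935 to 0.997 in I. Their verdict would be chosen after the data were seen. If instead everything below target counts as not promising, about half of cohorts with exactly the target activity are lost: 47% in A/H and 54% in I. The trial is meant to choose subtypes for later study, so either outcome would matter.

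**Working it through.** **Inputs (Cohort A, I and H sections; Phase II design).** n = 25 per cohort. Response priors: Beta(0.7, 1.3) for A/H and Beta(0.9, 1.1) for I. Targets 35% and 45%; failure rates 10% and 20%. Stop if Pr(p < target | data) > 0.95. With x responses in n patients the posterior is Beta(a + x, b + n − x).

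**The plan's own figure.** The 90% equal-tailed interval at the expected count:
- A/H: x = 25 × 0.35 = 8.75, posterior Beta(9.45, 17.55), width 0.2966 (stated 0.297).
- I: x = 25 × 0.45 = 11.25, posterior Beta(12.15, 14.85), width 0.3099 (stated 0.310).

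Both reproduce, so the priors and model are read correctly.

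**Stopping boundaries.** These are derived from the stated rule, because the boundary tables are not in the available text.

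| Look | A/H: stop at or below | I: stop at or below |
|---|---|---|
| 15 | 2 (13%) | 3 (20%) |
| 20 | 3 (15%) | 5 (25%) |
| 25, if applied | 5 (20%) | 7 (28%) |

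At 25 patients, Pr(p < 35%) is 0.9506 for 5 responses and 0.8857 for 6. Pr(p < 45%) is 0.9572 for 7 responses and 0.9046 for 8.

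**Are the 10%/20% limits left without a role?** Every boundary is at or above the matching failure rate, so an observed rate at or below 10% (A/H) or 20% (I) at a look always stops the cohort. A cohort that passes 20 patients has at least 4 (A/H) or 6 (I) responses, which is at least 4/25 = 16% or 6/25 = 24% at the end. It can no longer fall to the literal rejection limit. When the looks are followed, the stopping rule contains these limits and does not conflict with them.

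**Where the gap comes from.** An observed rate at or above target needs 9/25 = 36% (A/H) or 12/25 = 48% (I). That leaves 6–8 and 8–11 unlabelled. Exact binomial recursion over looks at 15, 20 and 25, efficacy rule only:

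| True response rate | Stopped | Unlabelled | At or above observed target |
|---|---|---|---|
| A/H 10% | 97.1% | 2.8% | 0.05% |
| A/H 35% | 11.2% | 35.6% | 53.2% |
| I 20% | 90.8% | 9.1% | 0.15% |
| I 45% | 9.2% | 45.1% | 45.7% |

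The middle column exists only if the cuts of 9 and 12 are imposed, and the document states neither. The 35% and 45% figures are the prior means (0.7/2 and 0.9/2), the thresholds in the stopping rule, and the assumed rates for the interval widths. They work as design parameters. An observed-rate cut placed at the true rate misses about half the time in any trial, so the 47% and 54% say little about this plan.

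**Reading promising as not stopped at 25.** Add the last two columns:
- A/H, at least 6/25: 2.8% + 0.05% ≈ 2.9% at a true 10%; 35.6% + 53.2% = 88.8% at 35%.
- I, at least 8/25: 0.0910 + 0.0015 = 0.0925, about 9.3%, at a true 20%; 0.4507 + 0.4573 = 90.8% at 45%.

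**Would a rule tied to the failure rate do better?** Requiring Pr(p > failure rate | data) > 0.95 gives at least 6/25 in A/H (0.983 at 6, 0.945 at 5). That is the same cut as surviving the plan's rule, so nothing changes in two of the three cohorts. In I it gives at least 9/25 (0.974 at 9, 0.935 at 8), with 4.4% false positives at 20% and 85.4% success at 45%. That buys about 5 points less error for about 5 points less success.

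**The case for a change.** The strongest case for acting is that the document never says promising means not stopped, and words such as rejected and promising ought to have a rule fixed before the data. That is true: no sentence settles it. Nor is it settled whether the 0.95 rule is applied at 25. If it is not, passing the looks at 15 and 20 is a weaker filter. It lets through 1 − 0.8918 = 10.8% of A/H cohorts at a true 10% and 1 − 0.8203 = 18.0% of I cohorts at a true 20%, and the unlabelled share under the observed-target reading rises to 39.3% and 47.3% at target. The missing boundary tables may answer this, so their absence cannot be held against the plan.

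The endpoint point is also factually right. The rates are stated at two cycles while the primary objective is best response. But the plan says openly that two-cycle response steers accrual and best response is estimated, so a formal test on the primary endpoint was not promised. Phase II design halts enrolment for want of responses, whereas Population for Analysis and Protocol Monitoring let accrual continue, and Protocol Monitoring calls its efficacy review non-binding. That is a separate inconsistency about how looks are run, and it does not show that the final classification is wrong.

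A rule based on exceeding the failure rate also has a cost. In A/H it would be met at 6/25 = 24%, below the 28–38% the Cohort A section cites for mTORC1 inhibitors. About 46% of A/H cohorts with a true rate of 22.5% would meet it, an awkward fit with a goal of finding high response rates. The same leniency applies to reading promising as not stopped in A/H, which is why the estimate and its interval need to inform selection alongside any label.

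**Conclusion.** The concern does not call for a change. The arithmetic is correct, but the gap appears only when an observed cut of 9/25 or 12/25 is read into a sentence that does not state one. Taking the plan's stopping criteria as its decision rule, applied at 25, every result is classified. Error is 2.9% (A/H) and about 9.3% (I) at the failure rates, success is 88.8% and 90.8% at the targets, and the rejection limits lie inside the stopping boundaries. What survives is an unwritten definition that analysts can fill sensibly, alongside the posterior estimate and 90% interval. The only alternative that alters a decision is the stricter cut in I (4.4% and 85.4%, against about 9.3% and 90.8%), which is a matter of preference.

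These figures assume binding looks at 15, 20 and 25, exactly 25 evaluable patients, two-cycle response as the monitored outcome, and no toxicity stops. The 5/25 boundary in A/H is close (0.9506), so it depends on the rule being computed without rounding down.

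### The interval widths of 0.297 and 0.310 that support 25 patients per cohort are widths at the expected response count, not the maxima the plan says they are

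*Combined protocol and SAP*

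**What the plan says.** In the Phase II design section, the sample size for cohorts A and H is tied to interval precision. The section presents 25 patients as a guarantee, for any cohort that runs to completion, that "a posterior 90% credibility interval for overall response rate will have width of 0.297 at most". The condition it attaches is a response rate of 35%. The prior for the response rate in these cohorts is Beta(0.7, 1.3).

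Cohort I has a parallel guarantee, again for 25 patients and no early stop, where the limit reads "width of 0.310 at most, under the assumption of a 45% of OR rate". Its response prior is Beta(0.9, 1.1).

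Response is monitored after 15 patients and then every 5. A cohort stops if the posterior probability that the response rate is below target (35% in A and H, 45% in I) exceeds 0.95. Dose modification for toxicity is monitored alongside, and the section states: "Independence was assumed between OR and Reason for dose modification".

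**The concern.** Both sentences are worded as guarantees with an upper limit. With a fixed sample size and prior, however, the posterior width depends on the number of responses and is greatest near one half. A width evaluated at 35% therefore cannot be an upper limit while higher response counts remain possible, and they are quite likely when the true rate is 35%.

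In the text available for this review, the precision statement is the only quantitative reason given for 25 patients per cohort. A reader would take from it that a completed cohort A or H will not give an interval wider than 0.297. The cases where that fails, 9 to 16 responses, are mostly the more encouraging results, which the trial means to use in choosing subtypes for later studies.

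**Working it through.** **Inputs (all from the Phase II design section).** n = 25 per cohort; response priors Beta(0.7, 1.3) for A and H and Beta(0.9, 1.1) for I; assumed rates 35% and 45%; 90% interval; futility stop if Prob(rate < target | data) > 0.95; looks at 15 and 20 before the full 25.

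**Formula.** With x responses in 25 the posterior is Beta(a + x, b + 25 − x). The equal-tailed 90% width is its 95th percentile minus its 5th.

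**Reproducing the plan's figures.**

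- A and H: x = 25 × 0.35 = 8.75, posterior Beta(9.45, 17.55), 0.5047 − 0.2081 = 0.2966, which rounds to 0.297.
- I: x = 25 × 0.45 = 11.25, posterior Beta(12.15, 14.85), 0.6071 − 0.2972 = 0.3099, which rounds to 0.310.

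So the plan's numbers are correctly calculated, but at fractional counts. A highest-density interval gives 0.2955 at 8.75, so the A/H figure is the equal-tailed one.

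**Widths at attainable counts.**

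| Responses of 25 | A and H | I |
|---|---|---|
| 8 | 0.2904 | 0.2922 |
| 9 | 0.2984 | 0.2998 |
| 10 | 0.3045 | 0.3055 |
| 11 | 0.3086 | 0.3092 |
| 12 | 0.3109 | 0.3112 |
| 13 | **0.3115** | **0.3113** |
| 14 | 0.3102 | 0.3098 |
| 15 | 0.3072 | 0.3064 |
| 16 | 0.3023 | 0.3011 |
| 17 | 0.2955 | 0.2939 |

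In A and H every count from 9 to 16 exceeds 0.297; the largest excess is 0.3115 − 0.297 = 0.0145. In I only 12 and 13 exceed 0.310; the largest excess is 0.3113 − 0.310 = 0.0013. For any posterior whose two parameters sum to 27 (25 patients plus a prior weight of 2), the width cannot exceed 0.3115.

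**How often the stated limits fail.** The futility rule gives these boundaries:

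- A and H: stop at 2 or fewer of 15 (posterior probability 0.970; 0.900 at 3) and at 3 or fewer of 20 (0.977; 0.930 at 4).
- I: stop at 3 or fewer of 15 (0.975; 0.923 at 4) and at 5 or fewer of 20 (0.965; 0.911 at 6).

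Under the plan's independence assumption, toxicity stopping does not change the distribution of responses among cohorts that reach 25. Exact binomial calculation then gives:

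- A and H, true rate 35%: P(reach 25) = 0.9254; P(reach 25 and width > 0.297) = 0.5311; conditional share 0.5311 / 0.9254 = 57.4%.
- I, true rate 45%: P(reach 25) = 0.9305; P(reach 25 and width > 0.310) = 0.2746; conditional share 0.2746 / 0.9305 = 29.5%.

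With no early stopping the shares are 53.2% and 27.5%. If the boundary is also applied at 25, or at 5 and 10, or both, they are 60% to 63% and 30% to 31%. Early stopping raises the share because it removes low counts, which have narrow intervals.

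**The case against.** The strongest reply is that neither sentence claims an unconditional maximum. Each is conditional on the assumed rate, and at that rate the figures are right to three decimals. This does not rescue the upper limit. If the condition refers to the true rate, the observed count still varies and the limit fails as shown. If it refers to the observed rate, there is only one width and nothing to bound; moreover 35% of 25 is not a whole number, and 9 of 25 already gives 0.2984.

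Other points stand and limit the finding:

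- The fault lies in the wording, not the calculation.
- The figures do not flatter typical precision. Among cohorts that pass the looks at 15 and 20, the mean width is 0.294 in A and H and 0.306 in I, both below the stated values.
- Of the 57.4%, about 17.6 points come from 9 of 25 alone, where the excess is only 0.2984 − 0.297 = 0.0014. Without that count the share is 39.8%. An excess of more than 0.01 occurs in about 24%.
- With highest-density intervals, 9 of 25 gives 0.2975, so that count becomes borderline.
- No stopping rule or analysis uses either width.

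**Conclusion.** The concern holds. Neither 0.297 nor 0.310 is a maximum; the true maxima at 25 patients are 0.3115 (A and H) and 0.3113 (I). At its own assumed rate, the A/H limit is exceeded in 57% of cohorts that reach 25. That figure rests on equal-tailed intervals, the stated priors and stopping rule, looks at 15 and 20, and independence of response and dose modification; it stays above one half under every look schedule tried. The statement that more than half fail applies to A and H only.

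The practical effect is small: at most 0.0145 in A and H, about 5% of the stated width (0.0145 / 0.297 = 0.049), and negligible in I. This is a desirable correction to a stated design property, not a threat to the trial.

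**What to change.** Amend the two precision sentences in the Phase II design section. Either of these would do:

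- State one limit that is true for all three cohorts: with 25 patients, the equal-tailed 90% credible interval is no wider than 0.312, whatever the number of responses.
- Drop the upper-limit wording and give widths at attainable counts: about 0.298 if 9 of 25 respond (A and H) and about 0.309 if 11 of 25 respond (I).

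In either case, say that the interval is equal-tailed.

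The cost is two slightly less favourable descriptions of precision. Sample size, priors, stopping rules and analyses do not change. Keeping the present figures as true maxima would instead need 28 patients in each of A and H for 0.297, and 26 in I for 0.310; the gain would not justify that.
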